### 3.2. Specific Aims & Hypotheses.

Aim 1. Test the effects of CBTw + SE compared to a time and format matched active control of psychoeducation + SE on competitive work outcomes across the 9 month study period. A total of 276 unemployed Veterans with SMI will be randomized to CBTw + SE or the control arm of psychoeducation + SE. Assessed at posttreatment (12 weeks), 6 months (primary endpoint), 9 months and 12 months (to examine sustained effects), the primary outcome will be total weeks worked in competitive jobs. A secondary work outcome, achievement of steady competitive work (i.e. working at least 50% of the follow-up), will be compared between study arms across the 12 month follow up.

Hypothesis 1: Compared to the control arm, participants in the CBTw + SE arm will work significantly more weeks and will be more likely to become steady workers.

Aim 2. Test the effects of CBTw + SE compared to the control arm of psychoeducation + SE on health and recovery at posttreatment (12 weeks), 6 month and 9 month follow up periods. The study will determine the effectiveness of CBTw to improve key health and recovery outcomes including health-related quality of life, suicidal ideation, subjective recovery, symptoms, and mental health service utilization.

Hypothesis 2a: Compared to controls, participants in the CBTw + SE arm will have greater improvement on subjective recovery and health-related quality of life, and decreases in mental health symptoms, suicidal ideation, and inpatient service utilization.

Hypothesis 2b: Greater participation in competitive work will predict improvements in these outcomes over time.

Aim 3. Guided by the RE-AIM implementation framework, conduct an implementation evaluation of CBTw to inform future wide scale roll-out of the intervention across the VHA. Existing Vocational Rehabilitation Counselors (VRCs) at the 3 VA SE programs will deliver CBTw, supported by an initial implementation strategy bundle—site tailored implementation planning, CBTw training, and weekly consultation including audit and feedback. Informed by the RE-AIM implementation framework, data will be collected and utilized to tailor implementation during the study, with assessment of the following RE-AIM domains:

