#### *Aim 1 Competitive Work Outcome Measures: Collected Monthly*

The competitive work outcomes are gold standard in VA work studies. In Aim 1, the primary outcome is total weeks worked in competitive jobs. The secondary work outcome is steady competitive work status, defined as working at least 50% of the study period (at least 19.5 weeks out of 38 weeks). Also standard procedure in work studies and used in CBTw pilots, work outcomes will be collected monthly by onsite RAs via Veteran self-report monthly work update form (Appendix 8), and verified with CAPRI/CPRS/JLV SE notes (i.e. SE staff notes will be reviewed for data regarding hours and weeks worked) and directly with SE staff using a data collection form (Appendix 9), as needed. Additional verification layers will be used under any of the following conditions: monthly work update forms are not fully completed; conflicting or unclear information is reported (e.g., Veteran reported only working two days during a month when s/he is employed full time); Veterans report having difficulty recalling their work during the past month. Work outcomes may be collected in person or by phone.

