#### *Competitive Work Outcomes (Hypothesis 1)*

For the outcome, total weeks worked in competitive jobs, three-level linear regression models will be used to test the effects of CBTw + SE compared to psychoeducation + SE over time, with predictors of study arm, arm by time interaction, site, and interaction between site and key predictors, covariates, as well as random effects to accommodate the potential non-independence due to repeated measures and group cohort effects. The time effects could be linear or nonlinear; these possibilities will be examined by treating time as continuous or categorical. If the outcomes are not normally distributed, robust maximum likelihood estimation method will be used to correct the standard error estimates for nonnormality. In the case of excess of zeros for this outcome, hurdle negative binomial models, a reliable method to analyze zero inflated longitudinal data of this nature, will be utilized. For the binary outcome, steady competitive work status across the 12-month study period, two-level logistic regression model will be used with the same set of predictors as in the linear models, with random effects to accommodate the potential non-independence due to group cohort effects.

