Aim 1: Work outcomes. The primary analysis is intention-to-treat and the primary outcome is total weeks worked in competitive jobs with primary endpoints of 6 and 9 months. Power estimate for total weeks worked was calculated using simulated data from a three-level linear regression model to account for the nested structure of the data. Simulation studies are the most flexible method for power analysis which can be tailored to any kinds of analyses. SAS 9.4 was used to generate 1000 datasets from each hypothesized model with plausible effect sizes for parameters of interest based on pilot data. Power estimates are based on the percentage of the datasets (replications) in which the parameters were significant. Based on the open trial pilot data, an ICC of .077 was estimated for the clustering effect of cohort and an ICC of .2 for repeated measures. Our pilot data show that CBTw significantly increased total weeks worked at 6 months ($f^2 = .15$). It is anticipated that there will be a larger increase in total weeks worked over time for the treatment arm. With the target sample size, there will be 97.6% power to detect even a small study arm by time interaction effect ($f^2 = .03$) with type I error set at .05. Further, the outcome distribution is likely to be non-normal. Although power will be attenuated by this non-normality, power to detect the target effects is still expected to be sufficient (>80%). For the binary outcome of achievement of steady competitive work, CBTw pilot data show that 49% of participants who were unemployed at baseline became steady workers at 6 months. In WORKWELL, it is expected that 5-10% more participants will acquire work and become steady workers during by the 9 month follow-up. Thus, power estimates may be conservative. In the control arm, it is anticipated that approximately 34% will become competitively employed and a lesser number will be steady workers by 9 months, based on VHA program evaluation data reporting 1-year SE outcomes. Based on the effect size, simulated data was used from two level logistic regression models, finding that the target sample size will provide > 99% power to detect the treatment effect, accounting for a conservative estimate of 13% attrition. If more participants gain competitive employed in the control arm (~50%), there will be >80% power to detect this effect.

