Hypothesis 1: For the outcome, total weeks worked in competitive jobs, three-level linear regression models will be used to test the effects of CBTw + SE compared to psychoeducation + SE over time, with predictors of study arm, arm by time interaction, site, and interaction between site and key predictors, covariates, as well as random effects to accommodate the potential non-independence due to repeated measures and group cohort effects. The time effects could be linear or nonlinear; these possibilities will be examined by treating time as continuous or categorical. If the outcomes are not normally distributed, robust maximum likelihood estimation method will be used to correct the standard error estimates for nonnormality. In the case of excess of zeros for this outcome, hurdle negative binomial models, a reliable method to analyze zero inflated longitudinal data of this nature, will be utilized. For the binary outcome, steady competitive work status across the 9-month study period, two-level logistic regression model will be used with the same set of predictors as in the linear models, with random effects to accommodate the potential non-independence due to group cohort effects.

Aim 2 Analyses: Health and Recovery Outcomes

To test **Hypothesis 2a**, Two-level linear regression models accounting for the nested nature of the data (repeated measures nested within individuals) will be used to examine the effects of CBTw + SE services compared to psychoeducation + SE on the change of each of the continuous outcomes including recovery (RAS), health-related quality of life (PCS & MCS), symptoms (DSM), and suicidality (SSI) over time (baseline and 3-, 6-, 9-months follow-ups). The scores of the outcome measures are calculated by averaging the corresponding items. The models are the same as those in Aim 1 analysis except that the outcomes are different. It is hypothesized that CBTw + SE will lead to a greater improvement on the health and recovery outcomes (indicated by a significant arm by time effect). If the outcomes are not normally distributed, robust maximum likelihood estimation method will be used to correct the standard error estimates for nonnormality.

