To test **Hypothesis 2b**, two-level linear regression models will examine the effects of work on health and recovery outcomes over time, with predictors of competitive weeks worked, time, weeks by time interaction, site membership and potential interaction between site and key predictors, potential covariates (i.e. controlling for baseline levels of health and recovery), as well as random effects to accommodate the potential non-independence due to repeated measures and group cohort effects.

Missing data: Aims 1 & 2

Missing data from Aims 1 and 2 will come in two different forms: missing by attrition and intermittent missing of observation. Using logistic regression, the effects of missing observations due to sample attrition will be examined by investigating the participant characteristics associated with dropout. If results reveal that data are missing completely at random (MCAR) or due to observed factors (MAR), the data will be analyzed using full information maximum likelihood, taking into account potential predictors for missingness. However, if the pattern of missing data is nonignorable, pattern-mixture models that includes variables defined by the participant's pattern of missing data will be used. Sensitivity analyses also will be performed to examine how the result will change based on different assumptions about the missing data, such as the missing work period having no work, the mean amount of work as available data from earlier follow-up periods, or full employment.

Account for Heterogeneity in the Sample

The study is limited to working aged Veterans with SMI who are unemployed at baseline, decreasing the heterogeneity of the sample. In addition, analyses will examine whether treatment effect will change as a function of the site membership and major characteristics of the study participants, such as different types of SMI diagnoses, age, and current substance use (e.g., users vs. non-users).

AIM 3 CBTw IMPLEMENTATION: OVERVIEW

The initial CBTw implementation strategy was informed by implementation science and developed based on our experience in the two CBTw pilots, stakeholder surveys and interviews, and feedback from operational partners. *In order to ensure successful implementation of CBTw during WORKWELL and wide-scale uptake following its completion, an evaluation of this initial implementation strategy and barriers and facilitators of implementation will be conducted, guided by the RE-AIM framework.*

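### Steady work has no primary scoring rule for a Veteran whose window is only partly observed, and the default missing-data method then amounts to a completer analysis

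*SAP*

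**What the plan says.** The protocol's Aim 1 measures section defines steady work as "defined as working at least 50% of the study period" and gives the threshold as "at least 19.5 weeks out of 38 weeks". Section 3.2 words it as "achievement of steady competitive work (i.e. working at least 50% of the follow-up" and places the comparison over 12 months. The protocol's analysis section models "steady competitive work status across the 12-month study period"; the SAP uses 9 months: "For the binary outcome, steady competitive work status across the 9-month study period, two-level logistic regression model will be used". Both use a two-level logistic model, Veteran within group cohort.

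Work is collected monthly. Incomplete or unclear forms are checked against SE notes and SE staff. Under protocol 5.7, withdrawn Veterans complete no outstanding assessments, and dis-enrolling from SE ends participation.

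The SAP's section on missing data for Aims 1 and 2 says that if data are missing completely at random or because of observed factors, "the data will be analyzed using full information maximum likelihood, taking into account potential predictors for missingness". Pattern-mixture models follow if missingness is nonignorable. Three fills for missing work periods (no work, mean of earlier work, full employment) are listed as sensitivity analyses. The power statement for steady work is described as "accounting for a conservative estimate of 13% attrition".

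**The concern.** A status that compares weeks worked with half of a fixed window cannot always be read off a partial record. Neither document says what to do then. Likelihood methods do use partial histories for the repeated weeks-worked outcome, but steady work has no repeated-measures level to draw on. The analyst must therefore drop the Veteran, count the observed weeks as they stand, or fill the gap, and the plan does not name one of these as primary.

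Leaving may well be related to having found, or failed to find, a job. If so, each arm's steady-work rate is biased among completers. The arm difference is biased too if leaving works differently in the two arms. A choice made after the data are seen could also move the result.

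**Working it through.** **1. Expected loss.** 0.13 × 276 = 35.9, about 36. Per arm, 138 × 0.87 = 120 completers and 18 leavers if loss is equal.

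**2. The plan's own figure.** The SAP gives more than 99% power for steady work. This cannot be reproduced, because the control steady rate is not stated; it is only said to be below the 34% expected to be employed. As a reference, take 49% (CBTw pilot, 6 months) against 34%, 120 per arm, two-sided 0.05 (assumed), no clustering:

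z = (0.15 × √120 − 1.96 × √(2 × 0.415 × 0.585)) / √(0.49 × 0.51 + 0.34 × 0.66) = (1.643 − 1.366) / 0.689 = 0.40, so power is 66%.

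At 49% CBTw, 99% power needs a control steady rate of at most about 23%, or about 18% with design effect 1 + 7 × 0.077 = 1.539. The SAP's wording allows either, so this step shows no error.

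**3. What likelihood recovers.** For a Veteran with covariates x and a missing outcome y, the contribution within cohort is P(y=0|x) + P(y=1|x) = 1. It carries no information on the arm effect. Monthly work would have to enter as an auxiliary variable, and the plan does not specify that.

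**4. When status is already settled.** Let w be the weeks worked by week t, W the window and T the threshold. The Veteran is steady once w ≥ T, and not steady once w + (W − t) < T. With W = 38 and T = 19.5, a never-worker is settled only after week 38 − 19.5 = 18.5, and nobody is settled before then. A never-worker at week 12 still has 26 weeks left. With leaving spread at random over 38 weeks, simulations put the settled share of leavers at 36 to 43%. If leaving clusters in the 12-week group phase, it is near zero. The documents give no leaving times, so the share cannot be computed.

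**5. Extreme scorings.** Assume 49% and 34% among 120 completers per arm, with 18 leavers per arm.

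| Leavers | CBTw | Control | Difference |
|---|---|---|---|
| Dropped | 49.0% | 34.0% | 15.0 |
| All not steady | 58.8/138 = 42.6% | 40.8/138 = 29.6% | 13.0 |
| All steady | 76.8/138 = 55.7% | 58.8/138 = 42.6% | 13.0 |
| Opposite by arm | 42.6% or 55.7% | 42.6% or 29.6% | 0.0 or 26.1 |

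**6. Unequal loss under no effect.** Let the true rate be 34% in both arms (0.34 × 138 = 46.9 steady), with 10 CBTw and 26 control leavers, all non-steady. Completers show 46.9/128 = 36.7% against 46.9/112 = 41.9%, a false gap of 5.2 points.

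**7. Simulated work histories** (38 weeks, 200,000 Veterans per arm; all work and leaving rates assumed). Set A: 40% of controls and 68% of CBTw ever start a job, weekly job loss 1.2 to 1.5%, re-entry 5% per week, true rates about 31% and 59%. Set B: true rates about 32% and 53%. Work-dependent leaving is three times as likely in one state as in the other. Attrition in set A is about 13% with random leaving and 14 to 18% when leaving is more likely while working.

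| Leaving | Completer rates, error per arm | Difference when observed weeks are counted against 19.5 |
|---|---|---|
| Random | not the issue | A: 28.2 to 25.8; B: 21.8 to 19.7 |
| More while working | A: 3.0 and 3.7 too low; B: 3.0 and 3.3 too low | A: 28.5 to 24.1; B: 22.2 to 19.0 |
| More while not working | A: about 2 too high; B: 2.6 to 2.7 too high | not reported |

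The error in the completer difference is the CBTw error minus the control error. With the same pattern in both arms, it is 3.7 − 3.0 = 0.7 points in A and 0.3 in B. In a further set with a true difference of about 21.5 points, the shift was at most about 0.2 points with the same pattern and a fall of 2 to 3 points when the pattern differed by arm. Exchanging the arms' patterns reverses the sign. Across the sets, counting observed weeks cost about 1.5 to 5 points.

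**8. Window and threshold.** Half of 38 is 19; 19.5 is half of 39; half of 52 is 26. The printed threshold does not match its own window, and neither fits the 12-month wording.

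**The case against.** The strongest reply is that the plan does address missing data. It names pattern-mixture models for nonignorable loss, takes predictors of missingness into account, lists three fills, and uses SE notes and staff to complete monthly forms. Work to date could enter as a predictor, the 13% is called conservative, and fewer than 36 Veterans may lack a status. All of this is fair, and it limits the size of the problem. It does not supply a primary rule. The dropout regressions look at participant characteristics and cannot establish that missingness is nonignorable. Leaving that depends on monthly work is ignorable only once monthly work is in the model.

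Three stronger readings are tempting, and the documents do not support them.

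- A reader might infer that leavers are excluded even when their status is known. No text says so, and the 19.5-week definition would allow such Veterans to be scored.
- A reader might see a broken intention-to-treat promise. The SAP's sentence "The primary analysis is intention-to-treat" concerns the primary analysis, and steady work is secondary.
- A reader might take section 3.2 to mean half of each Veteran's own follow-up. The same sentence refers to the 12-month follow-up, so the trial's fixed period is the natural meaning.

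It is also true that the completer difference hardly moves when leaving depends on work in the same way in both arms. Counting observed weeks against 19.5 is not the plan's stated primary rule; it resembles the no-work sensitivity fill.

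**Conclusion.** The gap is real and its likely effect is modest. No primary rule scores a partly observed window, and the default method is in effect a completer analysis for this outcome. Under the assumed histories, each arm's rate is about 2 to 3 points off (up to 3.7 in one set) when leaving depends on work. The arm difference moves by less than 1 point if the pattern is shared and by about 2 to 3 points if it is not. Scoring observed weeks as they stand costs about 1.5 to 5 points.

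These sizes rest on assumed job-start, job-loss and leaving rates. Set A takes 40% of controls ever starting a job, where the SAP expects about 34% employed, and its 59% for CBTw is the top of the SAP's implied 54 to 59%. The scorings in steps 5 and 6 are bounds, not forecasts. The change should be made before unblinded analysis. It concerns a secondary outcome and does not touch total weeks worked.

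**What to change.** In the SAP's Aim 1 analysis and missing-data sections:

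1. State one window and one threshold for steady work. Reconcile 9 months (SAP) with 12 months (protocol 3.2 and analysis section), and 19.5 with 38 weeks. Say that the denominator is the fixed window.
2. Score a Veteran steady once observed weeks reach the threshold, and not steady once it can no longer be reached.
3. For the rest, multiply impute the remaining months' weeks from monthly work to date, arm, site and work history, then apply the threshold and fit the planned logistic model.
4. Keep the no-work, mean-work and full-employment fills as sensitivity analyses, with the first and last as bounds.

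The cost is SAP wording, matching protocol wording, and a short program using monthly data already collected. The downside is reliance on an imputation model for the unresolved Veterans. Their number depends on when they leave and is at most about 13% if attrition is as planned.

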#### *Health and Recovery Outcomes (Hypotheses 2a & 2b)*

To test **Hypothesis 2a**, three-level linear regression models (i.e. mixed models) accounting for the nested nature of the data will be used to test the effects of CBTw + SE services compared to psychoeducation + SE on each of the continuous outcomes including recovery (RAS), health-related quality of life (PCS & MCS), symptoms (CCSM), and suicidality (SSI) over time. For the count outcome of service utilization, three level Poisson regressions will be used to examine group differences over time on number of days of inpatient hospitalization. If there is a problem of excess of zeros for utilization (e.g., no hospitalizations), hurdle negative binomial models will be used.

To test **Hypothesis 2b**, three-level linear regression models will examine the effects of work on health and recovery outcomes over time, with predictors of competitive weeks worked, time, weeks by time interaction, site membership and potential interaction between site and key predictors, potential covariates (i.e. controlling for baseline levels of health and recovery), as well as random effects to accommodate the potential non-independence due to repeated measures and group cohort effects.

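### The SAP's Hypothesis 2a model leaves out the group-cohort level that the protocol and the SAP's own cross-reference to Aim 1 require, and the SAP has no analysis of inpatient days

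*SAP*

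**What the plan says.** **Hypothesis 2a.** The protocol (Data Analysis, Health and Recovery Outcomes) specifies "three-level linear regression models (i.e. mixed models) accounting for the nested nature of the data will be used". The SAP (Aim 2 Analyses) instead says "Two-level linear regression models accounting for the nested nature of the data (repeated measures nested within individuals) will be used", and its Aim 2 power paragraph describes the same two levels. A few sentences later the SAP adds: "The models are the same as those in Aim 1 analysis except that the outcomes are different". The Aim 1 model for weeks worked is three-level, with random effects for repeated measures and for group cohort. The effect tested in 2a is arm by time.

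**Hypothesis 2b.** The SAP says "two-level linear regression models will examine the effects of work on health and recovery outcomes over time", but the same sentence lists random effects for both repeated measures and group cohort. The protocol calls this model three-level.

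**Inpatient days.** Fewer inpatient services is part of Hypothesis 2a (protocol 3.2). The protocol says "three level Poisson regressions will be used to examine group differences over time on number of days of inpatient hospitalization", with hurdle negative binomial models if there are too many zeros. The SAP's Aim 2 outcome list covers recovery, the two SF-12 summaries, symptoms and suicidality. It has no inpatient outcome and no count model.

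**Delivery.** Both arms meet in groups of up to 8 (protocol 5.2.2), and CBTw cohorts are closed once formed. The baseline assessment is done before randomization (protocol 5.3.2).

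**The concern.** Veterans who share a group and its facilitators may change together. If the model does not know this, the standard error of the arm effect on change is too small, and improvements in recovery, quality of life, symptoms or suicidal ideation are declared too often.

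The SAP treats cohort as real elsewhere. In its Aim 1 power section "an ICC of .077 was estimated for the clustering effect of cohort", and the total sample size is said to allow for cohort clustering. As written, one analyst could fit visits within persons and another could fit the Aim 1 structure. Both could claim to follow the SAP, with different standard errors and p-values. A hypothesised outcome with no SAP analysis leaves a similar gap: whether and how it is reported is open.

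**Working it through.** **The plan's own figure.** The documents state no type I error for the Aim 2 models. The nearest figure is the Aim 1 power of 97.6% at f² = .03. It comes from a simulation whose variance components, number of visits and cohort sizes are not reported, so it cannot be reproduced uniquely. Two closed forms come close, taking power ≈ Φ(√λ − 1.96):
- 240 persons × 3 visits, repeated-measures design effect 1 + 2 × .2 = 1.4, no cohort term: λ = .03 × 720/1.4 = 15.43, power 97.5%.
- 276 × 4 visits, design effect 1 + 3 × .2 = 1.6, cohort design effect 1.462: λ = .03 × 1104/(1.6 × 1.462) = 14.16, power 96.4%.

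Other reasonable choices run from 71% to over 99%. The figure is neither confirmed nor refuted.

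**Inputs from the documents.** Error rate "with type I error set at .05" (sidedness not stated; two-sided assumed). From the pilot, in the Aim 1 power section, "an ICC of .077 was estimated for the clustering effect of cohort and an ICC of .2 for repeated measures". 138 per arm in groups of at most 8, so 138/8 ≈ 17 cohorts per arm. Attrition of 13%, so 8 × .87 ≈ 7 remain in a full group.

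**Assumptions.** Aim 2 cohort ICC of .02, .05 or .077. Groups near full (m = 7 or 8). Visits at 0, 3, 6 and 9 months. Stable person-level share of variance p from .123 to .5.

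**Step 1: a plain comparison of arms at one visit.** Design effect DE = 1 + (m − 1) × ICC; true error = 2[1 − Φ(1.96/√DE)]. At ICC .077:
- m = 8: DE = 1.539, error .114
- m = 7: DE = 1.462, error .105
- m = 5: DE = 1.308, error .087

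This is not the test that the SAP names for 2a.

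**Step 2: the arm-by-time test with linear time.** Set the total variance to 1. Centred times are −4.5, −1.5, 1.5 and 4.5, with sum of squares 45. Each person's slope has within-cohort variance (1 − p − ICC)/45. The cohort's contribution depends on when its effect acts:
- Constant from baseline: it cancels from every slope and contributes 0. Error stays at .05.
- Absent at baseline, full at all later visits: each cohort's slope shifts by 4.5/45 = .1 of its effect, variance .01 × ICC.
- Growing linearly to month 9: shift of 1/9, variance ICC/81.

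The ICC of the slopes is the cohort part over the total, and goes into the Step 1 formulas. With ICC .077 and m = 8:
- After baseline, p = .2: .00077/(.00077 + .01607) = .0457; DE 1.320; error .088.
- After baseline, p = .5: .00077/(.00077 + .00940) = .0757; DE 1.530; error .113.
- Growing, p = .2: .00095/(.00095 + .01607) = .0559; DE 1.391; error .097.
- Growing, p = .5: .00095/(.00095 + .00940) = .0918; DE 1.643; error .126.

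**Step 3: null simulations** (17 cohorts per arm, 6,000 to 20,000 replicates) of the arm-by-time test without a cohort level:

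| Cohort effect (linear time) | ICC | m | Simulated error |
|---|---|---|---|
| Constant over time | .077 | 7–8 | .047–.055 |
| Arises after baseline | .077 | 8 | .081–.120 |
| Grows over time | .077 | 8 | .092–.139 |
| Arises after baseline | .077 | 7 | .079–.109 |
| Grows over time | .077 | 7 | .090–.128 |
| Arises or grows | .05 | 8 | .075–.100 |
| Arises or grows | .02 | 8 | .060–.070 |

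With time as categories, which the SAP also allows, the joint test gave .075 to .118 at ICC .077 and m = 8 when the effect arises or grows.

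**Step 4: what corrects it.** Comparing cohort mean slopes between arms, on 2 × 17 − 2 = 32 degrees of freedom, gave .047 to .052 in the settings with a post-baseline cohort effect. A cohort random intercept would not do this. With balanced data arm-by-time is a within-person contrast, and a time-constant cohort term drops out of it just as it does in Step 2.

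**The case against.** The strongest reply is that the SAP has not removed clustering from Aim 2. Hypothesis 2b lists cohort random effects, and the sentence tying 2a to Aim 1 would bring them back there. That stands in part. A reader might infer that every Aim 2 model drops cohort, and the documents do not support that. What they show is a contradiction over 2a and a wrong label on 2b. The 2a wording is still hard to read as a slip: it names its two levels, and the power paragraph repeats them.

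A reader might also infer that the Aim 2 tests run at about twice their nominal error. The documents do not establish this. The ICC of .077 appears in the weeks-worked power paragraph and comes from an open CBTw pilot. None is given for the Aim 2 scales or for psychoeducation groups. Eight is a maximum, with no mean group size stated. The textbook formula in Step 1 fits a comparison at one visit, not arm by time. Nor does the figure carry over to 2b, whose predictor is each person's own weeks worked.

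It is also fair to say that returning to the protocol's three levels would not by itself cure the problem, because the protocol names no cohort-by-time term. And the claim of more than 80% Aim 2 power has not been shown to fail: its derivation is not given, and the Aim 1 figure at the same effect size may leave room.

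The SAP's robust estimation option does not fill the gap, since it is offered only for non-normality. On inpatient days the omission is real, but the protocol's model already has a fallback for excess zeros, so no different model is needed.

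**Conclusion.** The point holds as an unreconciled specification of the Aim 2 models, with a conditional effect on error rates. If 2a is fitted without cohort, its arm-by-time test could have a type I error of roughly .08 to .14. That rests on an Aim 2 cohort ICC near .077, groups of 7 or 8, linear time, and cohort effects that arise or grow after baseline. At an ICC of .02 to .05 the error is about .06 to .10. It is .05 if cohort effects are constant over time. Because baseline precedes randomization, effects that come from the group itself cannot be present at baseline, so some inflation is the likelier case; its size is not known.

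The omission of inpatient days from the SAP is plain from the text and needs no assumption.

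These are secondary outcomes, and the primary model keeps its cohort random effects. This should be fixed before analysis; it does not threaten the primary result.

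**What to change.** 1. State one three-level model for Hypothesis 2a (visits, persons, cohorts) and use the same description in the Aim 2 power paragraph and the analysis section.
2. Include a cohort random effect on post-baseline change, as a cohort-by-time or post-baseline cohort term. An intercept alone is not enough.
3. Use small-sample degrees of freedom based on the number of cohorts, about 34 in all if groups are full.
4. Relabel Hypothesis 2b as three-level, to match the random effects it already lists.
5. Restore the protocol's inpatient-days analysis, with its hurdle negative binomial option, or give the reason for dropping it.

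The cost is SAP wording and slightly wider intervals for these secondary outcomes. The models need no new outcome data, only a cohort identifier for each participant in the analysis file, which the Aim 1 model already requires.
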